1.2 Purpose

The primary purpose of this study is to assess the efficacy and safety of different maintenance dosing regimens in patients who have achieved a PASI 90 response after 24 weeks of treatment with secukinumab 300 mg s.c. The current study will assess if an extended dose interval (every 6 weeks vs every 4 weeks) will allow psoriasis patients who achieve PASI 90 after 24 weeks of secukinumab treatment to maintain this response for a further 28 weeks (52 weeks in total).

The study will also assess whether dose intensification through a shortened dose interval (every 2 weeks vs every 4 weeks) will allow patients who are PASI 75 responders but not PASI 90 responders after 24 weeks of treatment with secukinumab 300 mg s.c. to achieve the PASI 90 target after a further 28 weeks of treatment in the maintenance period. In addition, patient reported outcomes (PRO) data will be collected to explore the effect of secukinumab on health-related quality of life (HRQoL) and work productivity.

2 Study objectives

2.1 Primary objective

The primary objective is to demonstrate in the patient pool of PASI 90 responders at Week 24 that secukinumab 300 mg s.c. every 6 weeks treatment is non-inferior to secukinumab 300 mg s.c. every 4 weeks treatment with respect to maintaining a PASI 90 response rate at Week 52.

2.2 Secondary objectives

The key secondary objective is to demonstrate in the patient pool of PASI 75 responders who do not reach a PASI 90 response at Week 24 that secukinumab 300 mg s.c. administered

every 2 weeks is superior to secukinumab 300 mg s.c. administered every 4 weeks at Week 52 based on the PASI 90 response rate.

Other secondary objectives are as follows:

- Evaluate the proportion of PASI 50, PASI 75, PASI 100 and IGA mod 2011 0/1 responder rates at Week 52.
- Evaluate the course of mean PASI over time from Week 24 to Week 52.
- Evaluate the effect of different maintenance treatment frequencies on PROs: Dermatology Life Quality Index (DLQI), EuroQOL 5-Dimension Health Questionnaire (EQ-5D[©]), Work Productivity and Activity Impairment Questionnaire-Psoriasis (WPAI-PSO), and the patient's assessment of pain, itching and scaling.

2.3 Exploratory objectives

- Evaluate the proportion of PASI 50, PASI 75, PASI 90, PASI 100 and IGA mod 2011 0/1 responders at Week 24.
- Evaluate the time to achieve clear or almost clear skin based on PASI 90 when receiving secukinumab 300 mg s.c. every 2 weeks compared to every 4 weeks from Week 24 to Week 52.
- Evaluate time to first loss of PASI 75 response when receiving secukinumab every 2 weeks compared to every 4 weeks from Week 24 until Week 52.
- Evaluate the safety and tolerability of different maintenance treatment regimens of secukinumab 300 mg s.c.
- Explore the correlation between the pharmacokinetic (PK) data and efficacy outcomes.

Other exploratory objectives for patients with PASI 90 response at Week 24 are as follows:

- Assess the time to loss of PASI 90 response.
- Assess the time to loss of IGA mod 2011 0/1 response.

3 Investigational plan

3.1 Study design

This is a randomized, open-label with blinded-assessment, multicenter, 52-week study to evaluate the efficacy (based on PASI 90), safety and tolerability of secukinumab 300 mg s.c. in patients with moderate to severe chronic plaque psoriasis. This study consists of 2 treatment periods: a 24-week run-in treatment period (Baseline to Week 24) and a 28-week maintenance treatment period (Week 24 to Week 52) as indicated in Figure 3-1.

For Treatment Period 1 (Baseline to Week 24) all patients will receive the same treatment:

• Secukinumab 300 mg s.c. will be self-administered at Baseline, once weekly at Week 1, 2 and 3; and thereafter every 4 weeks starting from Week 4 (ie, Week 4, 8, 12, 16 and 20).

At Week 24, all patients will be assessed in term of PASI response and either randomized to one of the 4 treatment groups in Treatment Period 2 (Week 24 to Week 52) or withdrawn from the study.

Patients with at least a 90% reduction in PASI score from Baseline will be randomized at Week 24 on a 1:1 basis to Group 1 or Group 2:

- Group 1 (recommended maintenance treatment): secukinumab 300 mg s.c. every 4 weeks (Week 24, 28, 32, 36, 40, 44 and 48).
- Group 2 (experimental dosing maintenance treatment): secukinumab 300 mg s.c. every 6 weeks (Week 24, 30, 36, 42 and 48).

Patients with less than 90% reduction in PASI score from Baseline at Week 24 but who achieved at least a 75% reduction in PASI score from Baseline are eligible for dose frequency intensification and will be randomized on a 1:1 basis to either Group 3 or Group 4:

- Group 3 (recommended maintenance treatment): secukinumab s.c. 300 mg every 4 weeks (Week 24, 28, 32, 36, 40, 44 and 48).
- Group 4 (experimental maintenance treatment): secukinumab s.c. 300 mg every 2 weeks (Week 24, 26, 28, 30, 32, 34, 36, 38, 40, 42, 44, 46 and 48).

At Week 52, patients from Group 3 and Group 4 will enter into a treatment-free follow-up period until Week 60. From the last study drug administration at Week 48 to Week 60 (12 weeks) patients will not be allowed to take any study drug. At the Week 60 visit, relapse, rebound and safety will be explored.

At Week 24, patients with a reduction in PASI score from Baseline of less than 75% will not be eligible for randomization and will be discontinued from the study.

Randomization will be stratified by body weight collected at the Randomization Visit ($< 90 \text{ kg or } \ge 90 \text{ kg}$).

[figure not shown]
The study drug will be self-administered by patients throughout the study. Study drug administration will occur at the study center for all study visits in Treatment Period 1; and at the study center or at the patient's home in Treatment Period 2. Self-administrations at every study center visit should be supervised by the study center personnel to ensure a correct study drug application and proper preparation of the patient for the home administration without study center personal supervision. If needed a caregiver of the patient can be trained for home administration to provide support. Home drug administration using the same injection device (ie, pre-filled syringes [PFS]) was introduced in previous secukinumab Phase 3b clinical studies, eg the CAIN457A2312, CAIN457A2313, and CAIN457A3301 studies. To allow for comparable treatment group data at fixed study visits, patients will be trained for home drug administration prior to Treatment Period 2.

A blinded PASI assessor who has no access to the randomization details must perform all PASI and IGA mod 2011 efficacy assessments for Treatment Period 2 (Week 24 to Week 52). To reduce measurement variability it is recommended that the same blinded PASI assessor performs all PASI and IGA mod 2011 assessments for a single patient.

The blinded PASI assessor must not participate in any study-related activities that could compromise the blinding and should solely concentrate on the skin examination for PASI and IGA mod 2011 assessments. For more details please refer to Section 5.4.

Safety will be assessed throughout the study through the monitoring of AEs, SAEs, electrocardiograms (ECGs), vital signs and laboratory data.

Figure 3-1 Study design

- **★** randomization of responder (PASI ≥ 90)
- randomization of responder (75 ≤ PASI < 90)
- BL: baseline
- NR: non-responder (PASI < 50)
- PE: primary endpoint
- PR: partial responder (50 ≤ PASI < 75)

Page 24

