#### 1.4.3 Screening, baseline and post-baseline definitions

Screening refers to any procedures (e.g., checking inclusion and exclusion criteria) performed prior to the date of visit 2. Per protocol, subject informed consent must be obtained prior to performing any study related activity. The date of signing informed consent is the start date of screening period. Any assessment obtained during the screening period will be labeled screening assessment.

Visit 2 is defined as *Baseline* visit. All consecutive visits are labeled according to the preplanned study week where they occur, i.e. Week 1, Week 2, and so on.

Week 24 is defined as the end of Treatment Period 1 (visit 11) for patients without premature discontinuation during Treatment Period 1. For patients with premature termination within Treatment Period 1 the last visit is defined as end of Treatment Period 1.

Week 52 is defined as the end of Treatment Period 2 (visit 18) for patients without premature discontinuation during Treatment Period 2. For patients with premature termination in Treatment Period 2 the last visit is defined as end of Treatment Period 2.

Any visits and assessments occurring after the end of Treatment Period 2 visit (Week 52 in the eCRF) will be aligned to the Week 60 Follow-Up visit.

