#### 1.4.4 Analysis Visits windows

*Visit-windows* will be used for the data that is summarized by visit; they are based on the study evaluation schedule and comprise a set of days around the nominal visit day. The visit windows for Treatment Period 1 and Treatment Period 2 are shown in Table 1-3. In this table, the days are counted since the first dose of study treatment (study days).

When visit windows are used, all visits will be re-aligned, i.e., they will be mapped into one of the visit windows. E.g., if the *Week 4* visit of a subject is delayed and occurs on Day 46 instead of on Day 29, say, it will be re-aligned to visit window *Week 8*. In the case of major deviations from the visit schedule, or due to unscheduled visits, several assessments of a subject may fall in a particular visit window (either scheduled or unscheduled). Statistical approaches to handle multiple assessments in a given visit window are specified in Section 1.4.5.

Table 1-3 Analysis windows for scheduled visits

Analysis Visit	Week	Scheduled Day	Analysis Window
Screening	-4 to BSL		-28 days to Day 1
Baseline*	BSL	1	
Week 1	1	8	Day 2-11
Week 2	2	15	Day 12-18
Week 3	3	22	Day 19-25
Week 4	4	29	Day 26-43
Week 8	8	57	Day 44-71
Week 12	12	85	Day 72-99
Week 16	16	113	Day 100-127
Week 20	20	141	Day 128-155
Week 24	24	169	Day 156-183**
Week 28	28	197	Day 184-211
Week 32	32	225	Day 212-239
Week 36	36	253	Day 240-267
Week 40	40	281	Day 268-295
Week 44	44	309	Day 296-323
Week 48	48	337	Day 324-351
Week 52	52	365	Day 352-379

\* Baseline measurement before the first drug administration. The days are counted since the first dose of study treatment.

For parameters which are not collected at every visit (e.g. DLQI, WPAI-PSO), visit windows defined in Table 1-3 will be combined. For example, if a parameter is measured at Week 24, Week 36 and Week 48, but not in between (i.e. Week 28, Week 32, Week 40 and Week 44), the Week 36 visit window will extend from Day 212 to Day 295 (combining Week 32 to Week 40 visit windows). If more than one assessment falls into the interval, the rules defined in Section 1.4.5 below are applied.

Assessments from Treatment Period 2 will not be considered for Treatment Period 1 and Treatment Period 1 visits will not be mapped into Treatment Period 2. For example, if a Week 28 (scheduled visit) measurement falls into the Week 20 visit window, this measurement would not be analyzed as Treatment Period 1 value.

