• **Relapse**: when the achieved maximum PASI improvement from baseline is reduced by > 50%, i.e. relapse is defined as the following condition being fulfilled:

$$1 - \frac{\cdot i}{D_{max,i}^+} > 0.5$$

where  $D_i$  is the difference in PASI between Baseline and Week i and  $D^+_{\max,i}$  is the maximum improvement in PASI between Baseline and any visit prior to Week i.

Rebound: A patient will be considered to have experienced a rebound, if the PASI increases to ≥125% of Baseline PASI, or if new pustular psoriasis, new erythrodermic psoriasis, or more inflammatory psoriasis occurs within 8 weeks after the last dose of study treatment has been received. For the current study rebound is assessed at the end of the Follow-Up period (i.e. Week 60 in the visit window described in Section 1.4.4).

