# PASI 50/75/90/100 and IGA mod 2011 0 or 1 response over time in Treatment Period 2 and Follow-Up Period

Summary statistics for PASI 50/75/90/100 response and for IGA mod 2011 0 or 1 response from Week 24 to Week 52 will be presented for the FAS-P90R and the FAS-P75R separately in contingency tables including absolute and relative frequencies. For the FAS-P75R also the response rates at Week 60 will be provided. Risk differences between the dosing groups will also be provided.

Figures will be provided as well displaying estimates for responder rates by dosing group.

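### The SAP has no Week 60 analysis window, so an early unscheduled follow-up assessment can be reported as Week 60

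*Protocol*

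**What the plan says.** Protocol 3.1 sets the off-drug read-out for Groups 3 and 4: "From the last study drug administration at Week 48 to Week 60 (12 weeks) patients will not be allowed to take any study drug", and "At the Week 60 visit, relapse, rebound and safety will be explored". That text is not defective; it fixes the intended timing.

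The gap is in the SAP:

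- **Section 1.8.1.1** places the rebound assessment at "Week 60 in the visit window described in Section 1.4.4".
- **Section 1.4.4** says: "The visit windows for Treatment Period 1 and Treatment Period 2 are shown in Table 1-3". The last row of that table is Week 52, scheduled Day 365, window Day 352-379. It has no follow-up row.
- **Section 1.4.3** sets one rule for all later data, namely that anything "occurring after the end of Treatment Period 2 visit (Week 52 in the eCRF) will be aligned to the Week 60 Follow-Up visit". It gives no lower or upper day limit.
- **Section 1.2** admits to the Follow-Up Set (FUS) any Group 3 or 4 patient who entered follow-up and has some efficacy or safety data from it. Completing follow-up is not required.
- **Section 1.8.8** tabulates relapse and rebound in the FUS and in the per-protocol version, PP-FUS.
- **Section 1.8.7** adds response: "For the FAS-P75R also the response rates at Week 60 will be provided". It also carries the PASI score to Week 60 in the same set.

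**The concern.** A result labelled Week 60 should describe patients about 12 weeks off drug. The cross-reference in 1.8.1.1 leads to a window that is not there, and the rule in 1.4.3 applies the label to any later assessment, however early. The fault is therefore more than missing detail: followed as written, the rule gives a wrong label.

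The route to a wrong label is real but narrow. Protocol Table 6-1 schedules one follow-up visit, Week 60. It also provides for PASI and IGA at unscheduled visits and describes an unscheduled rebound assessment during post-treatment follow-up. A Group 3 or 4 patient who has such a visit soon after Week 52 and then leaves would be counted at Week 60 on that assessment.

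At stake are the off-drug comparison of Group 3 with Group 4 on relapse and rebound, and the Week 60 response rates and PASI scores in the FAS-P75R. All of these could mix different times off drug without the tables showing it.

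**Working it through.** **1. The plan's own figure.** In Table 1-3 every scheduled day equals 7 x week + 1.
- Week 48: 7 x 48 + 1 = Day 337.
- Week 60: 7 x 60 + 1 = Day 421.
- Time off drug: 421 - 337 = 84 days = 12.0 weeks. The protocol's 12 weeks is reproduced.

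**2. Earliest assessment that 1.4.3 labels Week 60.**
- On schedule, the Week 52 visit is Day 365, so the label starts at Day 366: 366 - 337 = 29 days, or 4.1 weeks off drug.
- At the edges of the protocol's ±5-day visit windows (dose on Day 342, Week 52 visit on Day 360), it starts at Day 361: 361 - 342 = 19 days.

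**3. Two rules for the same days.** With an on-schedule Week 52 visit, an assessment on Day 366-379 lies in the Week 52 window of Table 1-3 but is Week 60 under 1.4.3. The 1.4.3 sentence is the only explicit rule that keeps follow-up data out of Week 52. Suppose the Week 52 visit is on Day 360 and an unscheduled PASI is taken on Day 366. The distances from Day 365 are 5 days and 1 day. Without the sentence, a closest-to-schedule choice would take the follow-up value as Week 52, which is the key secondary time point in these groups.

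**4. A candidate window.** The 4-weekly visits from Week 8 onward use -13/+14 days. Around 84 days since last dose this gives 71 to 98 days (10.1 to 14.0 weeks), or Day 408-435 after a Day 337 dose. Visits within protocol tolerance all fall inside it: earliest 416 - 342 = 74 days, latest 426 - 332 = 94 days. A midpoint rule would be looser: (365 + 421)/2 = Day 393, so a window opening at Day 394 admits 394 - 337 = 57 days, only 8.1 weeks off drug.

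**5. Possible size, on assumed rates only.** Let f be the fraction scored early, r12 their relapse rate had they been seen at 12 weeks, and rE their rate at the early assessment. The reported rate shifts by f x (rE - r12). None of these inputs is in the documents. Take f as 2% to 20%, r12 as 20% to 40% and rE as 2% to 10%:
- smallest: 0.02 x (10 - 20) = -0.2 points;
- largest: 0.20 x (2 - 40) = -7.6 points.

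The negative sign comes from assuming rE below r12. For scale, Protocol 9.7.1 expects 105 patients per group, so one patient is 1/105 = 0.95 points. At an assumed relapse rate of 35%, the 95% half-width for the group difference is 1.96 x sqrt(2 x 0.35 x 0.65/105), about 13 points.

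**6. Rebound.** The definition in Protocol 6.4.3.1 and SAP 1.8.1.1 carries a limit of 8 weeks after the last dose: 337 + 56 = Day 393, or Week 56. The scheduled assessment is at Day 421. The limit could attach to the whole definition or only to the new forms of psoriasis; the text does not say which.

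**The case against.** The strongest reply is that this is a drafting gap with little reach, and much of that stands.

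- No early follow-up termination visit is scheduled. An early leaver is scored only if a discretionary unscheduled visit recorded PASI, IGA or rebound. Otherwise the value is missing and, under SAP 1.8.3, not replaced. For most patients the 1.4.3 sentence simply labels the one planned visit.
- The closest-assessment rule in SAP 1.4.5 should select the true Week 60 visit when there is one. It does nothing for a patient with only an early assessment, and Table 1-3 gives it no Week 60 target day.
- PP-FUS may remove such patients from relapse and rebound. However, its criteria are left to a later data review, the FUS result is still reported, and the FAS-P75R Week 60 tables have no such filter.
- Relapse and rebound are additional exploratory variables. Week 60 response is additional secondary, and Week 60 PASI is an add-on to a secondary time course. None is in the confirmatory hierarchy.

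A reader might infer that relapse is understated, and more so in the arm with more early leavers. The documents do not support a direction. Unscheduled visits prompted by worsening would be enriched for relapse, and a patient already in relapse is probably classified correctly. Patients who stop drug during Treatment Period 2 return for Week 60 on an unspecified schedule (Protocol 5.5.10), so their time off drug could exceed 12 weeks. For rebound, assessments at Week 53 to 56 lie inside the definition's own 8-week limit, so calling them too early is doubtful.

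**Conclusion.** The point holds as a minor inconsistency in the SAP. The Week 60 window cited in 1.8.1.1 does not exist. As written, the rule in 1.4.3 reports an early unscheduled assessment as Week 60 from about 4 weeks off drug (29 days on schedule, 19 at the visit-window extremes) instead of 12. It affects the FUS relapse and rebound tables and the FAS-P75R Week 60 response and PASI tables.

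It applies only to Group 3 or 4 patients whose sole follow-up efficacy assessment was early, and they are likely to be few. The 0.2 to 7.6 points above illustrate scale under assumed rates and are not an estimate of bias. Nor can it be concluded that early leavers in general are scored at a shorter time off drug: those without an unscheduled efficacy assessment are simply missing. The primary and key secondary Week 52 analyses are unaffected by the present text.

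**What to change.** 1. Add a Week 60 analysis window anchored on days since last dose: target 84 days, for example -13/+14 days (71 to 98). Correct the cross-reference in SAP 1.8.1.1. A fixed study-day window could misplace patients who stopped drug early.
2. Keep the 1.4.3 sentence but amend it: assessments after the end-of-Treatment-Period-2 visit are never mapped to Week 52, and count as Week 60 only if inside the new window. Deleting it would open the problem in step 3 of the working.
3. Treat patients with no in-window assessment as missing at Week 60, whatever their earlier status. Counting early relapsers as events while setting early non-relapsers to missing would bias relapse upward. List relapses and rebounds seen earlier separately, as events at any time in follow-up.
4. Report actual time off drug and the number out of window, by group.
5. Reconcile the 8-week limit in the rebound definition with the Week 60 assessment, and state which parts of the definition the limit covers.

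The cost is a table row, a few amended sentences and a short listing. A few patients become missing at Week 60, including some whose last dose was earlier than Week 48. For example, with a last dose at Week 44 (Day 309) and a visit on Day 421, time off drug is 421 - 309 = 112 days, outside the window. Patients dosed and seen within the protocol's visit tolerances are not lost.

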3.2 Rationale of study design

The secukinumab 300 mg s.c. every 4 weeks dose regimen has been evaluated extensively in a Phase 3 clinical trial program and showed strong sustainability of efficacy response with a good safety profile up to 52 weeks of treatment. Further knowledge for long term maintenance treatment flexibility for the optimal effective dose is a medical need that dermatologists are looking for with any biologic psoriasis drug in order to administer to the patient the right dose and regimen at the right treatment time.

The main reason for choosing the study design is to research in optimized maintenance treatment options to minimize drug exposure for secukinumab in patients cleared or almost cleared (PASI 90) from psoriasis while maintaining an acceptable clinical response and comparable safety profile.

Another reason for the study design is to examine if PASI 75 responders could benefit in terms of efficacy from an increased dosing interval for the study drug with a comparable safety profile. In the CAIN457A2212 study psoriasis patients have been exposed to an increased drug exposure without detection of any safety-related signals.

Taken together the rationale for the study is to explore options for individualizing maintenance treatment.

The CAIN457A2304 study, part of the secukinumab Phase 3 program, has assessed a RAN (retreatment at the start of relapse) approach as an alternative to maintain treatment response in some patients when secukinumab response has been achieved after 12 weeks. The fixed-dose interval regimen every 4 weeks was shown to have a clear benefit compared to the RAN regimen for sustained efficacy in the treatment of psoriasis (Mrowietz et al 2013).

At the present time, there is still a need for clinical study designs assessing flexible dosing options for long-term biologic treatment of psoriasis for patients who have achieved clear or almost clear skin under treatment, and additionally, when a certain drug response is achieved that could be optimized towards complete clearance of the symptoms. This more individualized maintenance treatment has become a treatment option to assess for secukinumab 300 mg s.c. since it has shown speed, strength and sustainability with 74.3% of biologic naïve psoriasis patients achieving PASI 90 at Week 24. At Week 52, 81.8% of the patients who achieved PASI 90 at Week 24 maintained clear or almost clear skin from psoriasis showing a high level of treatment sustainability in the maintenance period. Pooled data from the Phase 3 studies showed that 87.6% of biologic-naïve patients achieved at least the PASI 75 criterion at Week 24 (95% confidence interval (CI) ranged from 84.7% to 90.1%) and could therefore be regarded as responders to secukinumab. At Week 24, 5.9% of patients achieved a PASI 50 partial response but no PASI 75 response and therefore did not fully benefit from secukinumab, while 6.5% of patients were non-responders.

This study is designed to assess the primary objective of allowing more treatment flexibility (extended dose interval to every 6 weeks) with less drug exposure in moderate to severe psoriasis patients who achieved a PASI 90 response after 24 weeks of secukinumab 300 mg s.c. Furthermore, this study is designed to assess the key secondary objective of allowing more treatment flexibility (shortened treatment interval to 2 weeks) in moderate to severe psoriasis patients who achieved a PASI 75 but not a PASI 90 response after 24 weeks of secukinumab 300 mg s.c. every 4 weeks. The study will also evaluate the safety and

tolerability of secukinumab. In addition, the study will collect data on PROs to explore the effect of secukinumab 300 mg s.c. maintenance treatment on patient's health related quality of life and work productivity.

In this study, only secukinumab verum injections will be administered. This will more closely reflect a real-life situation for patients than, for example, using a double-blinded, double dummy study design that would require secukinumab placebo injections. The blinded assessor approach is enabling to capture cogent efficacy data deriving from Investigator assessments. In addition, the design supports for interpreting these Investigator assessments in the context of a patient's daily life and social function measured by PROs (EMEA/CHMP/EWP/139391/2004).

The treatment-free follow-up period will be limited to treatment Group 3 and Group 4 as treatment-free follow-up period data for drug exposures up to 300 mg s.c. every 4 weeks in the maintenance phase have already been extensively reported for the Phase 3 secukinumab program studies.

Rationale for choice of non-inferiority margin and primary endpoint

Statistical projections to support the choice of non-inferiority margin for this study are difficult as Week 24 to Week 52 data are not available for PASI 90 response rates in patients treated with the experimental dosing frequencies scheduled for this study. However, for the active controlled study CAIN457A2304 in the secukinumab development program the non-inferiority margin was set to 15%. Based on clinical judgment, a non-inferiority margin of 15% is justifiable also, especially when taking into account the maintenance phase endpoint and the maintenance responder rate (ie, 81.8% of patients achieving a PASI 90 response at Week 24 are still PASI 90 responders at Week 52) observed in the clinical trial program with secukinumab 300 mg s.c. to date. This non-inferiority margin has been accepted for the CAIN4572304 study by participating regulatory agencies in the US, EU and Japan.

Similar study designs for drug exposure reduction for other biologic treatments in moderate to severe psoriasis patients are very limited. In the rheumatoid arthritis indication, non-inferiority margins in studies with drug exposure reductions have been recently accepted up to a 20% non-inferiority margin for efficacy endpoints (den Broeder et al 2013, Mariette et al 2014).

The non-inferiority margin for the primary endpoint is also comparable to other efficacy endpoints of the mentioned studies and is considered a clinically balanced choice taking into account the likelihood to maintain a PASI 90 response rate in the study population treated with a prolonged dosing regimen (secukinumab Phase 3 program, pooled data of biologic naïve patients). It should be noted in this context that the PASI scoring system, even if used as one of the most frequent ones to assess psoriasis drug efficacy in clinical trials, is known to be complex and a certain measurement system variability applies (Costa de Faria et al 2010).

Sample size details are provided in Section 9.7.

